## **2). Interim Analyses**

Interim analysis of the data will be conducted when 50% of the sample in each group is accrued and has had the opportunity to complete the 4-week intervention. We plan to continue data collection unless interim analyses indicate overwhelming significant effects regarding study aims.

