**Participants:** A power analysis was performed to estimate optimal sample size for detecting potential differences between intervention and wait-list control groups in sedentary behavior using a repeated measures design, with an alpha of 0.05, a power of 0.80, and a medium effect (0.57). Results from the G-power analysis indicated a total of 68 participants (34 per group) would be needed for the proposed study but we have increased sample size in anticipation of a potential attrition rate of approximately 20% (a minimum of 80 adults older than 55 yrs will be recruited). Four counties (Rock, Iowa, Vilas & Dane) will each recruit between 20–30 older adults who will be randomized to either the intervention group ( $n = 10–15$ ) or the control group ( $n = 10–15$ ). Inclusion criteria includes > 55 yrs, currently inactive or low active (i.e., < 60 min of physical activity/week), residents of Rock, Iowa, Vilas or Dane Counties, and residing in a home or an apartment. Exclusion criteria are low levels of sedentary behavior (i.e.,  $\leq 6$  hours/day); recent hospitalization (past month); uncontrolled medical conditions including uncontrolled hypertension (BP > 170 systolic or 100 diastolic), heart disease (symptoms of angina with minimal exertion in the past month), actively receiving chemotherapy or palliative care for cancer, stage 4 liver disease (e.g., cirrhosis with ascites or encephalopathy or history of

bleeding esophageal varices), end-stage renal disease (on dialysis or creatine > 4), or end-stage pulmonary disease (dyspnea at rest or with minimal exertion); severe arthritis or any orthopedic condition that could be made worse by standing up and moving more; inability to stand up without assistance of another person; and inability to speak or hear spoken English. Participants will be given a gift card up to \$50 upon study completion (\$20 for participating in the study plus \$10 per each of three assessments).

Recruitment of Participants: Staff from Aging Units in the four counties will recruit older adults from their counties for this study. Recruitment strategies include announcements in senior newsletters, at congregate dining sites, churches, and medical clinics. In addition, announcements will be posted on Aging Unit websites, and flyers will be sent to mailing lists of older adults in the various counties. These strategies were used in our pilot research and worked well in recruiting the estimated sample size.

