*Demographic and Health History Questionnaire*: At baseline, participants will be asked to complete a questionnaire regarding health status and demographic information (date of birth, sex, race, ethnicity, education, and marital status), current physical activity, smoking status, and current alcohol intake.

*Mediators of Behavior Change*: As suggested by NIH reviewers, we have added selected mediators of behavior change. Participants will complete questionnaires assessing self-regulation strategies, self-efficacy, and outcome expectancies.

*Adherence to the Intervention and Outcome Assessments*: Adherence to the *Stand Up and Move More* intervention workshop will consist of participants attending at least 50% of the sessions. As for outcome assessments, adherence to wearing the accelerometers will be defined as wearing the monitors 4 out of 7 days.

*Analyses*: The primary sedentary behavior outcome variables include total sedentary time, time spent sitting in long bouts (i.e.,  $\geq 60$  minutes), and sit-to-stand transitions as measured by the activPAL. These outcomes will be examined adjusting for monitor wear time if wear time differs between groups. We will also be able to analyze changes in specific domains of sedentary behavior (e.g., watching TV, reading) from data obtained from the sedentary behavior questionnaire. A 2 (groups) x 3 trials (pre, post-1, and post-2) repeated measures ANOVA will be used to examine differences between groups in changes in sedentary behavior before and following the intervention and control conditions. Similarly, for the secondary variables of physical activity, functional performance, health-related quality of life, and mediators of behavior change, a series of 2 x 3 repeated measures ANOVA's will be performed. Significant main effects and interactions will be assessed with planned contrasts. Effect sizes will be calculated to examine the magnitude of differences between groups as well as the magnitude of change from pre to post-intervention according to methods described by Cohen. In addition,

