correlational analyses will be performed to examine the relationship between sedentary behavior and the secondary outcomes. Significance will be set at  $p < 0.05$ . {Note: since sample size was estimated for our primary outcome variable of sedentary behavior, we recognize the potential limitation of our sample for secondary outcomes. However, if one or more of the secondary outcomes shows a trend in the direction of significance and/or shows a moderate to large effect size, the number of participants can be expanded in subsequent research to address a specific hypothesis}.

*Note:* Multiple imputation will be used to account for missing data (and attrition) under a missing-at-random assumption using MICE package in R. Longitudinal models for the outcomes at the two post-intervention visits will adjust the pre-intervention value as a covariate and explicitly model changes in the outcomes over time. Intervention workshop will be included in the included model as a random effect to account for correlations in outcomes between subjects in the same workshop.

Feasibility: The feasibility of implementing the program by our community partners will be assessed after the refresher session (at 8 wks) via semi-structured interviews. The Aging Unit Directors and Health Program Facilitators will be interviewed and asked about their satisfaction with the intervention, the ease and difficulty of implementing the program, and their likelihood of sustaining the intervention outside of a research study {*Note: Aging Units offer evidence-based health promotion programs to older adults in their counties which are funded by the Older Americans Act (OAA). When a new health promotion program is shown to be evidence-based (i.e., effective, translatable), Aging Units can use OAA funding to support and sustain implementation of the program*}. Interviews will be transcribed and coded, classified, and organized into main themes using thematic analyses. Feasibility of completing the program by older adults will be assessed after the refresher session (at 8 wks) on the basis of program adherence (i.e., attendance) and participant satisfaction (brief questionnaire).

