[name] is an Associate Professor in the Sinclair School of Nursing at the University of Missouri. She conducts research on the physical, cognitive, and emotional functioning of older adults residing in long-term care facilities.

3). [name].  
Professor of Biostatistics  
Mayo Clinic College of Medicine  
Rochester, MN 55902  
Email: [[contact]](mailto:[contact])  
[contact]

[name] is a lead statistician in the Division of Biomedical Statistics and Informatics at the Mayo Clinic College of Medicine.

Conflict of Interest for DSMB's: There are no conflicts of interest as members of the DSMB are not affiliated with this study or with the investigators.

Protection of Confidentiality: Data will be reported in a blinded manner in the DSMB report, and the data and discussion with the DSMB will be confidential.

DSMB Responsibilities: The responsibilities of the DSMB for this study include:

- (a) review the research protocol, recruitment plan, and data and safety monitoring plan
- (b) recommend subject recruitment be initiated after receipt of a satisfactory protocol
- (c) evaluate the progress of the trial, recruitment, accrual and retention, participant risk vs benefit, performance of the trial sites, and other factors which may affect study outcome
- (d) consider factors external to the study when relevant information becomes available that may have an impact on the safety of the participants or ethics of the trial
- (e) review study performance, make recommendations and assist in the resolution of problems reported by the Principal Investigator
- (f) protect the safety of the study participants
- (g) report to NIA on the safety and progress of the trial
- (h) make recommendations to the NIA and the Principal Investigator concerning continuation, termination or other modifications of the trial based on the observed beneficial or adverse effects of the treatment under study
- (i) if appropriate, review interim analyses in accordance with stopping rules
- (j) ensure the confidentiality of the study data and the results of monitoring
- (k) assist NIA by commenting on any problems with study conduct, enrollment, sample size, and/or data collection

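### The 50% interim look can stop the trial for efficacy without a threshold, variable or time point, and the final test stays at an unadjusted 0.05

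*Combined protocol and SAP*

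**What the plan says.** The Safety chapter, under 2). Interim Analyses, places one look at the point where half of each group has been accrued and has had the chance to finish the four-week workshop. The rule for acting on it is one sentence: "We plan to continue data collection unless interim analyses indicate overwhelming significant effects regarding study aims".

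Four other places bear on it:

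- **Analyses** (Research Design and Methods): "Significance will be set at" p < 0.05, with no allowance for an earlier look.
- **Participants** (same chapter): the power analysis was run "with an alpha of 0.05, a power of 0.80, and a medium effect (0.57"), so the whole 0.05 is used. No interim look is mentioned.
- **Analyses**: "The primary sedentary behavior outcome variables include total sedentary time", and the sentence goes on to list long sitting bouts and sit-to-stand transitions. The comparison is a 2 x 3 repeated-measures ANOVA over baseline, week 4 and week 12.
- **DSMB Responsibilities**, item (i): "if appropriate, review interim analyses in accordance with stopping rules". Item (h) lets the board recommend termination on the basis of observed benefit. The contents list for the DSMB report includes efficacy only where applicable.

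**The concern.** A look that can end the trial for benefit is a second opportunity to declare success. If the final test still uses the full 0.05, the two opportunities together exceed 5% whatever interim threshold is used. The plan does not give that threshold, so the size of the excess is unknown.

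The trigger also refers to the study aims in the plural. Aim 1 covers three activPAL variables and several secondary domains. Aim 2 is feasibility, judged from interviews, attendance and satisfaction, with no significance test. Nobody could say in advance which result would stop the trial.

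Timing adds a practical problem. The look is tied to the four-week workshop, so some participants in it may not yet have reached week 12, which is one of the three time points in the primary comparison. The plan does not say whether people already enrolled would be followed to week 12 after an early stop.

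**Working it through.** **Inputs from the documents.** Alpha 0.05; power 0.80; effect 0.57; 34 per group before attrition; 40 per group recruited; one look at 50% of each group (20 of 40); final test at p < 0.05.

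**Assumptions, not stated in the documents.** Two-sided tests; information fraction t = 0.5 at the look; one outcome variable; a normal approximation.

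**Step 1: reproduce the plan's own figure.** The power analysis "indicated a total of 68 participants (34 per group) would be needed for the proposed study". Take 0.57 as a standardised mean difference, so f = 0.57/2 = 0.285. Use the between-groups test of a repeated-measures ANOVA with m = 3 measurements and an assumed correlation of 0.5 between them:

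λ = f² × N × m / [1 + (m − 1) × 0.5] = 0.285² × 68 × 3/2 = 8.28

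With 1 and 66 degrees of freedom this gives power 0.810. N = 66 gives 0.798. So 68 is reproduced, as a fixed design that spends all of 0.05 on a single final test.

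**Step 2: overall type I error with one look.** Let Z₁ and Z₂ be the interim and final statistics. Under the null they are bivariate normal with correlation √t = √0.5 = 0.707. With interim cut-off c₁ and final cut-off c₂ = 1.960,

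overall error = 1 − P(|Z₁| < c₁ and |Z₂| < c₂).

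| *Overwhelming* read as | c₁ | Overall error, final test at 0.05 |
|---|---|---|
| p < 0.001 | 3.291 | 5.02% |
| p < 0.005 | 2.807 | 5.2% |
| p < 0.01 | 2.576 | 5.5% |
| p < 0.025 | 2.241 | 6.4% |
| p < 0.05 | 1.960 | 8.3% |

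As a plain check, the error cannot exceed the sum of the two levels. At p < 0.001 the ceiling is therefore 0.05 + 0.001 = 5.1%.

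**Step 3: sensitivity to the timing of the information.** If week-12 data are incomplete, t falls below 0.5. With t = 0.33 the worst-case row becomes 8.8% and the p < 0.001 row 5.05%. The order of the readings does not change.

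**Step 4: boundaries that hold 5%.** The same formula is used with a reduced final level. Power is evaluated at the drift that gives a fixed design 80%, namely 1.960 + 0.842 = 2.80.

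| Interim / final p | Overall error | Power |
|---|---|---|
| 0.001 / 0.0498 | 5.00% | 80.0% |
| 0.005 / 0.048 (O'Brien-Fleming, rounded) | 4.99% | 79.7% |

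The larger loss is 80.0 − 79.7 = 0.3 points.

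**The case against.** The strongest reply is that *overwhelming* already signals a strict threshold. Read as p < 0.01 or stricter, it adds only about 0.02 to 0.5 points of error. There is also an unaffiliated three-member DSMB with a biostatistician, which reviews the protocol and advises on continuation. Both points stand and limit the seriousness. Neither supplies a threshold, a variable or a time point, and neither lowers the final 0.05.

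A reader might infer more than the documents support:

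- **That the trial's error rate is 8.3%.** This requires stopping at bare significance, which the wording makes unlikely. It is an upper end at half information, not the trial's known rate.
- **That the three primary variables make the figure far larger.** At an assumed correlation of 0.5, testing three variables once already gives about 12.6%. That multiplicity exists without any look and is not counted here.
- **That the look uses week-4 data only.** The section fixes the timing, not the data. Early enrollees could already have week-12 results.
- **That the board must follow rules that do not exist.** Item (i) is conditional. The most that can be said is that no rules appear in these documents.
- **That a stop would leave only 40 participants against the 68 required.** About 40 is the number accrued when the look falls due. The plan aims for 60 recruits in year one, so more could be enrolled by the time a result is available.
- **That a formal boundary would prevent an exaggerated estimate.** It would not. If the true effect is 0.57, a stop at 20 per arm on p < 0.005 gives an average estimate of about 1.05, although such a stop has only about a 14 to 16% chance of occurring. That bias comes with any early efficacy stop, including one under a proper boundary.

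**Conclusion.** The point holds. The plan combines an efficacy stop with an unadjusted final 0.05, so for one variable the overall error is above 5% under any interim threshold. How far above cannot be determined from the documents: about 5.02% to 5.5% for thresholds from p < 0.001 to p < 0.01, and 8.3% in the worst case. These figures assume two-sided tests and a look at half the information. The likely inflation is small. The firmer defect is that the decision is not prespecified: no threshold, variable or time point is named, and week-12 completion after a stop is not addressed. This should be corrected before the look takes place, and the correction is almost free.

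**What to change.** In the Interim Analyses section, choose one of two options:

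1. **No efficacy stop.** State that the 50% look is for safety and feasibility only. The final test stays at 0.05. This is the only option that also avoids the upward bias of an early-stopped estimate.
2. **A defined efficacy stop.** Name one variable and time point, for example the between-arm difference in activPAL total sedentary time at week 4. Give a two-look boundary that holds 5%: p < 0.001 then p < 0.0498, or O'Brien-Fleming p < 0.005 then p < 0.048. Put the matching final level in the Analyses section and have DSMB item (i) refer to this rule. These pairs assume half the information at the look, so say that the final level will be recalculated if the actual fraction differs.

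In either case, state that participants already enrolled complete the week-12 assessment.

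The cost is two or three sentences. Option 1 gives up the chance to stop early for benefit. Option 2 lowers the final threshold slightly and costs at most about 0.3 points of power. Neither option deals with testing three primary variables, which needs its own rule.

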## **3). Data Safety and Monitoring**

The UW-Madison will be the IRB of record and our community partners, the four directors and staff of the Aging Network who regularly offer health promotion programs to older adults in their counties, will receive human subjects training through the UW-Madison. The PI will be responsible for ensuring participants' safety on a daily basis. The DSMB will act in an advisory capacity to the NIA Director to monitor participants' safety, evaluate the progress of the study, review procedures for maintaining the confidentiality of data, and review the quality of data collection, management, and analyses.

Frequency of Data and Safety Monitoring: The data will be reviewed every 6 months throughout the duration of the study. The PI will be informed of serious AE as soon as they occur and will

notify the NIA and DSMB within 24 hours of notification. The DSMB will meet twice annually via conference call to review study progress, data quality, and participant safety.

Content of Data and Safety Monitoring Report: The content of the report will include: 1) study status, 2) demographic characteristics of enrolled participants, 3) enrollment and attrition statistics, 4) quality assurance and regulatory issues, descriptions of any AEs and/or SAEs, and 6) intervention efficacy (if applicable).

Data and Safety Monitoring Board Membership and Affiliation: The Data and Safety Monitoring Board (DSMB) is composed of three members and includes experts in or representatives of the fields of relevant clinical expertise, clinical trial methodology, and biostatistics:

1). [name]. (Chair of the DSMB)  
Professor of Internal Medicine, Gerontology & Geriatric Medicine  
Wake Forest School of Medicine  
Winston-Salem, NC 27157  
Email: [[contact]](mailto:[contact])  
[contact]

[name] is the Deputy Director of the Sticht Center on Aging at Wake Forest School of Medicine. She has a Ph.D. in exercise physiology and conducts research on the effects of exercise on various health outcomes in older adults (e.g., weight loss, weight regain, inflammation).

2). [name]., R.N.  
Associate Professor of Nursing  
Sinclair School of Nursing  
University of Missouri  
Columbia, MO 65211  
Email: [[contact]](mailto:[contact])  
[contact]

[name] is an Associate Professor in the Sinclair School of Nursing at the University of Missouri. She conducts research on the physical, cognitive, and emotional functioning of older adults residing in long-term care facilities.

3). [name].  
Professor of Biostatistics  
Mayo Clinic College of Medicine  
Rochester, MN 55902  
Email: [[contact]](mailto:[contact])  
[contact]

[name] is a lead statistician in the Division of Biomedical Statistics and Informatics at the Mayo Clinic College of Medicine.

Conflict of Interest for DSMB's: There are no conflicts of interest as members of the DSMB are not affiliated with this study or with the investigators.

Protection of Confidentiality: Data will be reported in a blinded manner in the DSMB report, and the data and discussion with the DSMB will be confidential.

DSMB Responsibilities: The responsibilities of the DSMB for this study include:

- (a) review the research protocol, recruitment plan, and data and safety monitoring plan
- (b) recommend subject recruitment be initiated after receipt of a satisfactory protocol
- (c) evaluate the progress of the trial, recruitment, accrual and retention, participant risk vs benefit, performance of the trial sites, and other factors which may affect study outcome
- (d) consider factors external to the study when relevant information becomes available that may have an impact on the safety of the participants or ethics of the trial
- (e) review study performance, make recommendations and assist in the resolution of problems reported by the Principal Investigator
- (f) protect the safety of the study participants
- (g) report to NIA on the safety and progress of the trial
- (h) make recommendations to the NIA and the Principal Investigator concerning continuation, termination or other modifications of the trial based on the observed beneficial or adverse effects of the treatment under study
- (i) if appropriate, review interim analyses in accordance with stopping rules
- (j) ensure the confidentiality of the study data and the results of monitoring
- (k) assist NIA by commenting on any problems with study conduct, enrollment, sample size, and/or data collection

## **DATA COLLECTION AND QUALITY ASSURANCE**

Data Collection: All study data will be collected solely for the research purposes of this study. Outcome assessments consisting of accelerometer, questionnaire and interview data, as well as the Short Physical Performance Battery (i.e., balance, gait speed & chair stands) will be assessed by research assistants from the UW-Madison who are blinded to group assignment (Note: every effort will be made to ensure the assessors remain blinded throughout the duration of the study). The research assistants including the PI ([name]) will travel to the county sites on designated days to collect data at baseline, after the 4-week intervention, and at follow-up (12 weeks). The research assistants will be trained by [name] to complete data assessments prior to data collection. Data collection forms will be standardized and the participant's ID number will be recorded on the forms (rather than their names). Source documents for each participant's data (i.e., participant binder) will be stored in a locked cabinet in [name] laboratory. Data will also be entered (using ID numbers only) by one of the research assistants into an electronic database using SPSS statistical computing environment. The data will be stored in a password protected area with firewall protection. Only designated personnel on the project will have access to the file and password.

Data Management: The UW-Madison is the lead site for this study. [name] will be responsible for data management including activities such as development and maintenance of study materials including a manual of procedures (MOP) and data collection forms; training and supervising research assistants during data collection; overseeing data management via a secure data management system; reviewing data entry for possible errors; and assisting with data analyses. The community partners will not be involved in collecting, storing or analyzing

the data. Their primary responsibilities include recruiting participants, facilitating the *Stand Up and Move More* workshops, and providing information (via a semi-structured interview) about the feasibility of implementing the workshops. The Steering Committee for this study will meet bi-weekly to discuss study progress, data management, and quality control (with additional conference calls as needed).

Quality Assurance: Quality control and monitoring will be performed by [name] and [name] (Community Research Associate). [name] will train and monitor the research assistants, and ensure quality control regarding all aspects of this study. [name] will provide the training and fidelity monitoring of our community partners. As noted previously, [name] has been involved in statewide coordination of evidence-based health promotion programs for older adults in Wisconsin for over 9 years. Part of her responsibilities have included training, overseeing, and fidelity monitoring for other health promotion programs (e.g., the “Chronic Disease Self-Management Program”). Instruction manuals with scripts for each workshop session will be provided to the health facilitators (and used during training) to maximize fidelity of delivery of sessions per our intervention protocol. The health facilitators will record any deviations from protocol which will be discussed via telephone calls with [name] and [name]. The facilitators will also be asked to record any suggested changes to the protocol which will be discussed at a team meeting following delivery of the workshops.

